**Table 3. Elements of Collaborative Care for Women Veterans (CCWV)**

Care management Functions	CCWV Element	Local Tailoring Options
Initial MH assessment of patients referred by PCP	Care manager conducts baseline MH assessments, medication history, and other relevant information collection	Site designates a local MH care manager (RN or social worker) who conducts some or all care management functions; sites choose from VA-approved assessment packages
Women with positive assessments offered treatment choice	Treatment choices for anxiety, depression, and PTSD are medications, primary care-based CALM CBT, or both	Site chooses integrated MH providers according to local availability (psychologist; social worker) for training in CALM CBT
Care management Functions	CCWV Element	Local Tailoring Options
Women with severity or complexity requiring specialty treatment assisted to access specialty resources	Care manager inquires about preferences for gender-specific services and provider gender; facilitates connection to most congruent locally available specialty services, and makes a warm handoff if possible; care manager follows up with patient to check on any missed appointments or group sessions	Referral can be made to co-located or distant specialty services as available at the site; care manager is familiar with locally available gender-specific groups and providers most experienced in treating women; same gender provider options identified ahead of time
Systematic monitoring of symptoms and treatment emergent problems	Care manager uses structured MH assessments for depression, anxiety disorders, and alcohol problems as well as symptom and side effects checklists to monitor treatment response; follows up to assure medication and/or CBT session compliance	Sites choose from VA-approved follow-up assessment options; site can choose to involve peer support for telephone check-in with patient and in-person chaperoning and escorting to various services
Patient education and activation	If the patient has chosen medication, care manager provides basic patient education and activation relevant to the primary diagnosis; if CBT is chosen the care manager facilitates connection to an integrated provider trained in CALM	Site decides which materials from available care management programs care manager will offer; if in the scope of practice of the locally chosen care manager (e.g., MSW) the care manager may be trained to provide CALM CBT
Decision support	Care manager uses a stepped care protocol under supervision of a local psychiatrist to determine when decisions to increase or change treatment options are needed and to collect information to assist the primary care provider in making adjustments	Decision support templates may be locally selected from VA-approved options; sites choose a supervising psychiatrist who may be co-located or based in specialty mental health depending on local circumstances

Site 1: Because this project's Co-PI ([name]) is based at the San Diego PBRN site, we have already laid the groundwork for implementation at this site, in collaboration with the PBRN Site Lead, [name], who is the WH Medical Director. VA San Diego is an interesting and complex site at which to implement CCWV, because PC is delivered in two locations (La Jolla and Mission Valley) that serve both men and women, with 41 designated WH providers across the healthcare system. These two locations differ in their PC-MHI teams, with one having a clinical psychologist, a nurse case manager, and a part-time (1/8) psychiatrist; and the other having two psychologists, a nurse case manager, a part-time (6/8) psychiatrist, and psychology trainee time (approx. 40 hours/week). Unless the PCP is prescribing him/herself, most PC patients with MH needs are referred to the Anxiety Disorders Clinic or the Mood Clinic, unless the diagnosis is PTSD, in which case women are referred to the women's trauma clinic. *These clinics all have waiting lists.* MH providers at the two PC sites have expressed to the co-PI that CCWV would be an important and needed addition to the services currently provided, especially in that, for those who need a higher level of care, it can provide a "bridge" to that care and may even circumvent the need for such care if desired outcomes are achieved through CCWV. This site has a strong peer support specialist program, led by the Local Recovery Coordinator who has expressed her support for this study and will actively "market" the availability of female peer support specialists to the WH PCPs and patients. Of note, across the two PC clinics from Oct 2014 – Apr 2015, there have been 688 unique encounters in primary care by women with anxiety or depression. This substantiates that we will have sufficient numbers of women at this site to ensure that at least 130 will be referred to the CCWV care manager (see power analysis section) and will complete the baseline measures.

Pre-implementation (Aim 1 cont.): At each site, a local CCWV champion will be identified by the Site Lead when s/he signs onto the project. The CCWV package will be further developed and locally tailored, with attention to training and technical assistance needed at each site. Once prepared, the package will be piloted locally to ensure that it works as intended with local systems and processes. In order to use the CALM CBT platform, we are collaborating with [name] (see LoS) who will provide us with a VA version of the platform when it is ready (their CREATE study). Using the TECH, any challenges with pilot implementation will be discussed and addressed by the team. When the team determines that challenges have been sufficiently addressed, orientation meetings will be held with the broader clinic, where the CCWV package will be distributed, discussed, and marketed.

Implementation (Aim 2): The implementation phase will begin at one PBRN sites and will last a total of 15 months to ensure adequate time for patient Exposure to the care model as well as implementation evaluation and reach. CCWV will spread to three additional PBRN sites in the following years. PBRN representatives will be trained in CALM. Field notes will be taken during the training and minutes will be kept of all conference calls and meetings. Notes will be analyzed using ATLAS.ti and will be interpreted in conjunction with other evaluation data as described below. During regular implementation meetings, TECH will be used to assess and address implementation challenges.

Procedures: Once training is complete and sites are ready for implementation, women Veterans with possible depression and/or anxiety disorders will be referred by their PCP (or other referring provider) to the locally identified CCWV care manager, who will also conduct local case finding activities to identify women Veterans who may benefit from care management. The care manager will then complete a clinical evaluation to identify the disorder of primary clinical focus (Panic Disorder with or without Agoraphobia, Social Anxiety Disorder, Generalized Anxiety Disorder, Posttraumatic Stress

Disorder, depression). CCWV is an innovative care model that is proactive, patient-centered and personalized to each woman that has an appointment with the care manager. Specifically, the care manager assists the patient in deciding which type of treatment she wants to pursue (CBT, medication, or both). During or shortly after the initial meeting with the care manager, each woman will be asked by the RA if she is willing to participate in our research project, meaning that she will be asked to complete a brief written battery of measures (§3.3.3.3) and a short qualitative interview at baseline (after the first or second visit with the care manager) and at six-months post-baseline. Women who enroll after the baseline window will not be eligible for baseline survey measures; however they can participate in interviews. Participants who enroll in research after the baseline period, and any women who are otherwise unable or unwilling to complete the written surveys, will be invited to consent to participate in other components of the research (i.e., qualitative interviews, , data obtained from medical record).

For women who choose CBT, the CALM-trained provider will then meet with the patient weekly to review the CALM CBT modules. The program includes five general modules (introduction, psychoeducation, self- monitoring, breathing retraining and relapse prevention), and three other modules that are customized to each anxiety disorder (cognitive restructuring, in vivo exposure and interoceptive exposure), which are tailored to each anxiety disorder. Depression modules are also available. The CALM CBT platform is a computer-assisted delivery system. The provider sits with the patient in front of the computer and directs the individual to review the appropriate material, clarifying and individually tailoring. The program contains educational material as well as skills training and exposure exercises. The entire program is typically completed within eight 60-minutes sessions.

Maintenance and Evolution: The last phase in this framework allows us to take the feedback and make modifications to our implementation process to enhance CCWV adoption, fidelity to the REP framework, and dissemination to future sites. Sharing these details with stakeholders using TECH informs the current implementation process and sustainability for the future. The four REP phases allow us to account for each step of the guided implementation strategy. Finally, the interchange between these phases and the implementation process components provide an in-depth understanding of whether CCWV implementation requires further adaptation and customization prior to broader VA dissemination. During this phase, the research team will collaborate with the local implementation teams to develop points for the CCWV Implementation Playbook.

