## **5.2 Recruitment Methods**

This study involves both Veteran **Patients** (n=260; 65/site) and VA **Staff** participants (n=60; ~15/site).

**Patients.** Patient subjects will be recruited after making contact with the CCWV care manager via referral from their provider or other staff. The care manager will introduce the research study, and if the person wishes to find out more about the study and possibly participate, the care manager will introduce the Veteran to the RA (if available), ask the Veteran to complete the Research Candidate contact form, add research staff as an additional signer on their CPRS note to automatically notify research staff of interested individuals, or contact the RA through another secure HIPAA-compliant route such as phone call or encrypted email to relay the Veteran's referral information. . The RA will check in with the care manager frequently to learn when women Veterans have been referred, as well as respond to notifications from the CPRS system, phone calls, and encrypted emails. Using a visit-based sampling method, patients are eligible during their first or second visit with the care manager during the 15-month implementation period. The patient will be informed about the details of research participation and asked if they would like to participate in the project. If they agree, the written or verbal (if by phone) informed consent process will be conducted. Patients that are past the enrollment window (i.e., 1st or 2nd visit with care manager), or otherwise unable or unwilling to participate in surveys are still eligible to complete qualitative interviews.

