### ***Information from and about Veterans:***

Sources of patient data for this project include (1) Data obtained from medical records including utilization of MH and CCWV services, psychiatric medications, MH diagnoses, relevant patient history (i.e., MST), and symptom measures completed with care manager and obtained from medical record; (2) information provided by patient participants via surveys (baseline and six months) and interviews (baseline and six months; and (3) CALM modules accessed and/or completed. (

After consent, all enrolled participants in each project who enroll during the baseline window will complete a 30-45 minute survey, delivered in-person by a research assistant (RA) at baseline and six-months post-baseline. The surveys focus on patient activation, health-related quality of life, satisfaction with treatment, and project specific measures. In addition, a subset of approximately 45 women Veterans in each study will also be asked to complete an additional 30-minute qualitative interview with a research staff member at baseline and six months post-baseline. The participant will be asked to

complete a hard copy, which the RA will send via fax to a monitored fax machine at GLA to enter into the database. Participants who enroll in research after the baseline period, and any women who are otherwise unable or unwilling to complete the written surveys, will be invited to consent to participate in other components of the research (i.e., qualitative interviews, , data obtained from medical record), which may be conducted primarily by phone.

Patient semi-structured interviews will be coded only with a study ID, digitally audio-recorded, and uploaded to a secure VA server behind the VA firewall. If recording consent is denied, the researchers will take hand written notes, which will be securely transported and stored as described below until they are transcribed into an electronic format. When desired by the patient or the interviewer, or to accommodate the cognitive needs of the subject, the survey or interview can be performed at two or more sessions. At the end of the implementation period we will obtain utilization history through the Data Access Request Tracker (DART) system, conducting chart review in the VA Informatics and Computing Infrastructure (VINCI) environment.

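### The baseline survey comes after one or two care-manager visits, so six-month change in activation and quality of life is change from early engagement, and the models have no term for prior exposure

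*Combined protocol and SAP*

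**What the plan says.** The order of events is set out in the Procedures paragraph of Section 5.1 (Implementation, Aim 2) and in Section 5.2.

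- **Recruitment:** "Patient subjects will be recruited after making contact with the CCWV care manager".
- **Approach by research staff:** "During or shortly after the initial meeting with the care manager, each woman will be asked by the RA" whether she will take part.
- **Window:** "patients are eligible during their first or second visit with the care manager during the 15-month implementation period".
- **Survey:** the written battery is completed "at baseline (after the first or second visit with the care manager", and again six months after that baseline.
- **Content of the care-manager contact:** a clinical evaluation to identify the main disorder, after which "the care manager assists the patient in deciding which type of treatment she wants to pursue (CBT, medication, or both". Table 3 lists the initial assessment ("Care manager conducts baseline MH assessments, medication history, and other relevant information collection") and the offer of treatment as CCWV elements.

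Secondary aim (b) in Section 2.0 concerns change in symptoms, activation, quality of life and care experiences in relation to CCWV participation, and hypothesizes improvement. The impact-focused evaluation in Section 5.6 models change in activation, quality of life and care experiences from enrollment to six months, adjusting for patient, provider and site characteristics. The qualitative part of Section 5.6 also combines patient survey data with staff interviews to describe usual care at baseline.

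**The concern.** A change score attributed to a care model should start before the model does. Here the first measurement follows one or two contacts that belong to the model. Any movement in activation or quality of life between first contact and the survey goes into the baseline and drops out of the measured change. The amount of prior contact also varies between women, and no model term reflects it.

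The six-month change would then be reported as change with CCWV when it is change from some point shortly after CCWV began. A description of usual care that draws on these surveys has the same difficulty, because every respondent has already met the CCWV care manager.

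**Working it through.** The plan states no figure for this outcome that could be reproduced. The power analysis in Section 5.6 concerns a binary referral or retention outcome and gives no effect size, standard deviation or correlation for six-month change. The check is therefore a comparison of the sections, followed by a short piece of algebra.

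**Step 1: is there a survey before contact?** No. Section 5.1 (Pre-conditions) defers patient surveys to the implementation phase, and Section 5.2 recruits after contact. Section 5.2 places eligibility during the first or second visit, while Section 5.1 places the survey after it. On either wording contact has begun.

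**Step 2: what has happened by then?** The Procedures paragraph ties clinical evaluation and help with treatment choice to the care-manager appointment. Those two elements have begun by the survey. Table 3 also includes "care manager provides basic patient education and activation relevant to the primary diagnosis", but it gives no visit number and applies this to women who have chosen medication.

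**Step 3: does prior exposure vary?** Yes, by one visit at least. The window counts visits and sets no limit in days. The documents do not say whether a weekly CALM session may fall between visits 1 and 2. Days since first contact therefore carry information that visit number does not.

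**Step 4: does the model account for it?** Section 5.6 names patient, provider and site characteristics. It names neither visit number nor elapsed days.

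**Step 5: what does the change score estimate?** Let m(t) be the mean outcome t months after first care-manager contact, m(0) the mean just before contact, and s the time of the survey. Follow-up is six months after the survey.

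- Measured change = m(s + 6) − m(s)
- Change from before contact to the same follow-up = m(s + 6) − m(0)
- Difference (second minus first) = m(s) − m(0)

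Three cases follow:

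- m(s) = m(0): no bias.
- m(s) better than m(0), an early gain: measured improvement is too small.
- m(s) worse than m(0), an early decline: measured improvement is too large.

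If a share w of women are surveyed after visit 2, and g1 and g2 are the mean shifts by the survey after visits 1 and 2, the average difference is (1 − w) × g1 + w × g2. The documents give none of w, g1 or g2, so no number can be attached.

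**Step 6: which outcomes have an earlier measure?** Section 5.5 lists, among medical-record data, "symptom measures completed with care manager and obtained from medical record". With the initial assessment in Table 3, this may give an earlier symptom score. No such source is described for activation or quality of life, which come from the survey.

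**The case against.** The best defense is that the timing is openly defined, follows from recruiting through the care manager, and touches only secondary aims. Section 5.1 describes the study as mainly about implementation outcomes, and referral, adoption and reach do not use this baseline. All of that stands. It limits the importance of the point, but it does not supply the missing term or make the change score a pre-CCWV comparison.

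A reader might go further in five ways that the documents do not support.

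- **That the early visits have already activated the patient.** Table 3 attaches education and activation to women who chose medication and gives no visit number. For women who choose CBT, the care manager arranges the link to a CALM-trained provider. Only assessment and treatment choice can be placed before the survey.
- **That change is attenuated by some percentage.** Any such figure would be assumed. The bias could be zero or could run the other way.
- **That comparisons of change between sites are biased.** Comparing sites on change is not a stated aim, and adjustment for site characteristics may absorb part of any site difference in timing.
- **That care experience shows the same fault.** Experience of CCWV care cannot be rated before any contact, so a first measure after contact is needed there.
- **That the chart holds a true pre-treatment score.** Sites choose among approved assessment packages, so a common instrument is not assured, and nothing says women are untreated at referral. The chart score helps with symptoms only.

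It is also fair to say that the raw material for a remedy is already planned: Section 5.5 collects utilization of CCWV services, from which visit dates should be derivable. What is missing is their use in the analysis.

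**Conclusion.** The point holds for activation and health-related quality of life. As written, the plan measures change from early engagement, at one of two visit counts and an unstated number of days, and reads it as change with CCWV participation. That follows from the text alone and needs no assumption.

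The size and direction of any bias are unknown. A bias exists only if these outcomes move between first contact and the survey. The effect is confined to the secondary change analyses and to any description of usual care that relies on the baseline survey. This is an inexpensive improvement to secondary analyses and no threat to the implementation outcomes.

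**What to change.** Keep recruitment as it is, and make these changes to Section 5.6.

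1. For each baseline survey, derive or record the care-manager visit number and the days since first care-manager contact, using the CCWV utilization data already planned in Section 5.5.
2. Include both in the models for six-month change in activation and quality of life.
3. Add a sensitivity analysis limited to surveys completed at visit 1. State that this equalizes the visit count but does not remove prior exposure. State also that women surveyed after visit 2 have by definition returned once and may differ in engagement, so a difference between the two groups is not purely one of timing.
4. For symptoms, use the care manager's initial chart assessment as baseline where its instrument matches the follow-up measure.
5. Describe the activation and quality-of-life results as change from early engagement in CCWV, not from before it. Add the same caution where survey data feed the summary of usual care.

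The cost is two derived fields, one extra analysis and a more modest conclusion. Adjustment will not recover the change from before contact, because no survey was taken then; it shows whether the result depends on when the survey was done.

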## **Risk to Subjects**

This study involves both Veteran (520 total across sites) and VA Staff participants (60 total across sites).

### ***Veteran Involvement and Characteristics***

This 4-site project aims to inform the VA regarding implementation of collaborative care for women Veterans (CCWV). The study is primarily focused on implementation outcomes such as adoption, acceptability, feasibility, satisfaction, and reach, as well as patient engagement and retention; patient clinical outcomes (symptoms, etc.) though examined, are secondary. After IRB approval, at each participating site, we will enroll approximately 130 women Veterans who are referred by their primary care provider (PCP) or another referring provider to the CCWV care manager. Any woman referred to the care manager (and therefore initially screening positive for anxiety, depression, and/or PTSD) is eligible to participate. We will stop consenting enrollees once we have reached up to 80 women who have had an encounter with the care manager and who consent participate in the research, in order to complete data collection with 65 women at each site. Our goal is to have 260 women total (across the 4 sites) engaged in care management over the course of the study. Participation in CCWV consists of completion of the surveys, interviews, and access to relevant medical record data.

**Routine Clinical Care versus Research.** Meeting with the care manager and participating in Coordinated Anxiety Learning and Management (CALM), being followed by the care manager for medication adherence, psychiatric treatment and medication, or other mental health treatments are routine clinical care available to any woman Veteran seen at a participating primary care or women's health clinic. Consenting to research involves completing the research surveys, research interviews, and granting permission to access selected medical record data as part of an evaluation of the implementation outcomes and secondary clinical outcomes described above. Participants who enroll in research after the baseline period, and any women who are otherwise unable or unwilling to complete the written surveys, will be invited to consent to participate in other components of the research (i.e., qualitative interviews, data obtained from medical record). Patients do not have to consent to participating in research in order to receive routine clinical care with the care manager.

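### The patient sample size is 520 in one section and 260 in another, and enrolling about 130 women per site conflicts, as written, with a consent cap of 80

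*Combined protocol and SAP*

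**What the plan says.** All the relevant statements stand in current text of the combined protocol and SAP.

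- Section 5.1, Risk to Subjects, gives the number of Veterans involved: "This study involves both Veteran (520 total across sites".
- Section 5.1, Veteran Involvement and Characteristics, sets enrolment: "at each participating site, we will enroll approximately 130 women Veterans". The same paragraph then limits consent, "We will stop consenting enrollees once we have reached up to 80 women", and gives the reason: "in order to complete data collection with 65 women at each site". It closes with a further use of 260: "Our goal is to have 260 women total (across the 4 sites) engaged in care management".
- Section 5.2, Recruitment Methods, gives the patient sample as 260, with 65 per site.
- Section 5.1, in the Site 1 paragraph after Table 3, argues that the site has enough women so that "at least 130 will be referred to the CCWV care manager (see power analysis section) and will complete the baseline measures".
- Section 5.6, Power Analysis, uses n of at least 260, described as patients clustered within referring PCPs, at 4 sites. The number 130 does not occur there.

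**The concern.** A reader cannot tell from the plan how many women the study intends to enrol. One section counts 520 Veterans and another 260, and a single paragraph holds both an enrolment of about 130 per site and a stop to consent at up to 80. If enrolment means consent to research, a site that obeys the second sentence can never satisfy the first.

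Three things depend on the number. It is the participant count offered to those who judge the risk to human subjects. It is the target against which accrual is read. It also fixes how many women contribute data: the section on secondary data builds the VA record extraction from the list of women consented and enrolled. Finally, the power statement can be interpreted only if its n can be traced to one of the planned counts, and at present it cannot.

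**Working it through.** **Step 1. Reproduce the plan's own totals.** The inputs are the per-site numbers and the 4 sites.

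| Count | Per site | × 4 sites | Status of the total |
|---|---|---|---|
| Enrolled | about 130 | 520 | printed under Risk to Subjects |
| Consent cap | up to 80 | 320 | derived here, not printed |
| Completing data collection | 65 | 260 | printed in section 5.2 |

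Both printed totals follow exactly from their per-site numbers, so neither 520 nor 260 is an isolated slip. They come from two different per-site plans.

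**Step 2. Size of the disagreement.**

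- Enrolment against the cap, per site: 130 − 80 = 50 women; 130 / 80 = 1.625.
- Enrolment against the cap, in total: 520 − 320 = 200 women; 200 / 520 = 38%.
- Between the two printed totals: 520 / 260 = 2.

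**Step 3. Is the cap per site?** The sentence attaches *at each site* to the 65, not to the 80. If 80 were the cap for the whole study, it would lie below the 260 women meant to complete (80 < 260). Only the per-site reading leaves the sentence workable, so 320 rests on a well-supported inference.

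**Step 4. The 130 at Site 1.** Two texts bear on what the baseline measures are. The Procedures paragraph describes joining the research as "meaning that she will be asked to complete a brief written battery of measures" and an interview, at baseline and six months. Section 5.5 places the research survey after consent: "After consent, all enrolled participants in each project who enroll during the baseline window will complete a 30-45 minute survey". On that reading the baseline measures are research measures, and at most 80 consented women at a site could complete them, against the stated 130 or more. The cross-reference does not help, because the power analysis gives no 130.

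**Step 5. What n of at least 260 can mean in the power analysis.**

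- Level: as a total it equals 4 × 65 = 260 and agrees with section 5.2. As a per-site number it would mean 4 × 260 = 1,040 women, more than any other count in the plan. The total is the reading that fits, but the paragraph does not say so.
- Stage: the paragraph speaks of patients exposed to the care model, and elsewhere of session completion among all those referred. The matching 260 in section 5.2 comes from women who finish data collection. Referred, consented and completing women are different groups, and n is not assigned to any of them.

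**The case against.** The strongest reply is that the numbers form a funnel: about 130 referred per site, up to 80 consented, 65 completing. The enrolment sentence does tie the 130 to women referred to the care manager, and the next sentences speak separately of consent. This would reconcile every per-site figure, so a reader who infers that the numbers cannot be reconciled on any reading goes too far. What does not stand is that the plan says this. Its verb is *enroll*, the 520 are counted as participants, and the 130 at Site 1 are to complete baseline measures as well as be referred.

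A second reply is that the Site 1 measures may be clinical. Table 3 has the care manager carry out baseline mental health assessments as part of care, which no consent cap limits. That reading is open. The research reading is likelier, because the Procedures paragraph uses the word *measures* for the research battery at baseline. Even if the clinical reading is granted, the conflict between 520, the cap and 260 remains.

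A third reply is that the extra women are late enrollees who give only interviews or record access. They too consent after contact with the care manager, so they count toward the 80. They are also excluded from the baseline survey, so they cannot supply the 130 at Site 1.

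It is also fair to say that the power analysis does describe its n in part. What is missing is the level and the stage, not every description.

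**Conclusion.** The point holds. As written, the stated patient sample size is inconsistent: 520 participants in one place and 260 in another, with enrolment of about 130 per site beside a consent cap of 80. The gap is a factor of 2 between the printed totals, and 200 women between 520 and the cap. The figure of 320 assumes that the cap is per site. The statement that 130 women cannot complete the baseline measures under the cap assumes that these are the research survey.

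Two stronger conclusions might be inferred, and the documents support neither.

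- *The study is underpowered.* The power paragraph reports 0.80 at 8.78 PCPs per site, with alpha, the number of sites, a plausible range of 5% to 85% and an effect size variability of 0.05. It gives no retention difference to be detected, so the figure cannot be checked. That makes it unverified, not wrong.
- *The counts reveal a rate of loss to follow-up.* The plan pairs 65 only with 80, never with 130, and does not say that the step from 80 to 65 is attrition. The 80 may also include women who consented only to interviews or record access, so it is not the denominator for the six-month survey models.

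**What to change.** State one set of counts, per site and in total, and use it in every section: women referred; women consented, up to 80 per site (320 in total if the cap is per site); women completing data collection, 65 per site (260 in total). Say whether women who consent only to interviews or record access count toward the 80.

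Then correct three places: the 520 under Risk to Subjects, the enrolment of about 130 per site under Veteran Involvement and Characteristics, and the 130 in the Site 1 paragraph together with its reference to the power analysis. If 130 per site was meant as referrals, relabel it as such in each place and remove the statement that these women are enrolled or complete the baseline measures.

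In section 5.6, tie n to one of these counts and state that it is a total, if that is intended. Restate the power on that basis if it changes.

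The cost is a few text corrections and one check of the power calculation. If the restated power is lower, report it; nothing here calls for added enrolment.
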